## 3. Randomization

It was not pragmatic to randomize the behavioral health collaborative care intervention on the clinic/provider/patient level because clinics within a given geographic region of the health system have the same operations management team and share resources. Using computer generated random numbers, each region (cluster) was randomized to the order

of intervention roll out in 5 steps that occurred in 3 to 4-month intervals between April 2019 and May 2020.

#### **4. Anticipated Effect Size, Power and Sample Size**

In the investigators' prior study on the clinical effectiveness of electronic medical record clinical decision support (EMR-CDS usual care) for opioid prescribing, approximately 20% of patients on chronic opioid therapy had an average daily opioid dose  $\geq 50$  MEDD. Using equal baseline response rate (RR) for the usual care and behavioral health collaborative care groups, a total sample size of 372 patients are required to detect an odds ratio of 2.25, corresponding to a 50% decrease in the collaborative care group (RR=10% vs 20% in usual care), with 80% power. The total sample size averaged 11 patients in each study group within each of 35 clinics. In accordance with the cluster randomized design, the variance inflation factor  $1 + (m - 1)\rho$  was incorporated, where  $m$  is the average cluster size ( $m=11$ ) and  $\rho$  is the intra-cluster correlation coefficient ( $\rho \leq 0.03$ ). Applying this inflation factor and rounding up to allow for equal group sizes across clusters resulted in a total sample size of 490 patients - 245 per group. Accounting for a potential 15% attrition rate, 578 total patients - 289 per group - were needed to attain the target sample size required to detect a 50% decrease in proportion of patients with average daily opioid dose  $\geq 50$  MEDD in the collaborative care group compared to the usual care group.

#### **5. Statistical Analysis**

Outcomes data were observed and collected in two time periods, pre-index and post-index. For the behavioral health group, the index date was defined as the date of enrollment during the study recruitment period (April 2019 to December 2021). For EMR-CDS usual care group, the index date is the first date within the study enrollment period at which a patient had been prescribed opioid medications for 90 of the previous 120 days.

Potential participants in the control arm of the study were identified from the chronic opioid health maintenance registry within the electronic health record system and propensity score matched to patients enrolled in the behavioral health arm. Baseline variables in the propensity score model were age at index event date, sex, race/ethnicity, average MEDD, anxiety, depression, and Charlson comorbidity index score. Average MEDD was calculated from opioid medication orders in the 12-month pre-index period. MEDD is calculated by determining the total daily amount of a prescribed opioid, multiplying the dose of the opioid by a conversion factor to ascertain morphine milligram equivalents and then adding up the converted dosage. Anxiety, depression, and Charlson comorbidity scores were determined from pre-index encounter diagnoses, historical problem lists, and PHQ-9/GAD-7 scores  $>10$  documented within the electronic health record.

Study outcomes were observed and collected in two 12-month time periods defined relative to the index date, pre-index and post-index, resulting in a 2-dimensional vector of repeated measures for each outcome from each patient. All outcome models for repeated measures incorporate a random effect with unstructured covariance matrix to model within-patient variability. It was assumed that patients remained in the health system from their first observed encounter through the end of the study period. A difference-in-difference approach was utilized in which outcomes were assessed as the change in group differences from pre- to post-

index. The model included fixed effects for study group, time (pre-index, post-index), and the group-by-time interaction.

Repeat measured outcomes include average MEDD,  $\text{MEDD} \geq 50$ ,  $\text{MEDD} \geq 90$ , and service utilization (inpatient/emergency department). These repeated outcomes are evaluated using the generalized linear mixed model approach described above with fixed effects as defined for the model. MEDD categorial outcomes are evaluated via mixed effects logistic regression models with estimates of odds ratios and difference-in-difference ratios (ratio of odds ratios). Mixed effects negative binomial regression models are used for assessing group differences in service utilization with rate ratios and difference-in-difference ratios (ratio of rate ratios).

Outcomes defined by first-time documentation of guideline concordant care for opioid risk mitigation are also evaluated using logistic regression. These outcomes are not repeated measures as they are only assessed post-index among patients with no pre-index documentation. Thus, time effects and random patient effects are omitted from the generalized linear model when evaluating new occurrences of guideline concordant care for opioid risk mitigation. The resulting logistic regression models include a single fixed effect for study group and no random effects.

Analyses were carried out using SAS version 9.4 for Windows, group comparisons are evaluated at significance level 0.05, and all estimates are presented with 95% confidence intervals.

**Ochsner Clinic Foundation  
Institutional Review Board**  
[name]  
[contact] | [[contact]](mailto:[contact])  

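### CCM patients and matched controls are indexed by different rules, and nothing in the plan aligns calendar date or time on opioid therapy

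*SAP*

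**What the plan says.** SAP section 5 defines two time zeros. For the CCM group, "the index date was defined as the date of enrollment during the study recruitment period (April 2019 to December 2021". For usual-care controls, who come from the chronic opioid registry, "the index date is the first date within the study enrollment period at which a patient had been prescribed opioid medications" on at least 90 of the preceding 120 days. Each patient then contributes 12 months before and 12 months after their own index date.

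Controls are chosen by propensity score: "Baseline variables in the propensity score model were age at index event date, sex, race/ethnicity, average MEDD, anxiety, depression, and Charlson comorbidity index score". On dose, "Average MEDD was calculated from opioid medication orders in the 12-month pre-index period"; the denominator of that average is not given.

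For the repeated outcomes (average MEDD, the MEDD thresholds, hospital and emergency use), "The model included fixed effects for study group, time (pre-index, post-index), and the group-by-time interaction". Time here means before or after the patient's own index, not calendar time. The first-documentation outcomes (pain agreement, urine drug screen, naloxone and the others in SAP 1.4.1) are handled differently: "they are only assessed post-index among patients with no pre-index documentation", and "The resulting logistic regression models include a single fixed effect for study group and no random effects".

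Protocol C.8.1 promises covariates in general terms and names none; the SAP adds none.

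**The concern.** The control rule picks the earliest qualifying date in the window. A registry patient already on chronic opioids is indexed close to the opening, and one who becomes chronic during the window is indexed at about the start of chronic therapy. A CCM patient is indexed whenever referral and enrolment happen, which can be much later in both calendar time and course of treatment. Matching on pre-index MEDD aligns dose level, not date or stage of therapy. Randomisation does not help, because it fixed the order of regional rollout, whereas controls are selected from the registry.

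Two distortions follow. If documentation or prescribing habits changed between 2019 and 2022, the groups are observed under different conditions. If the groups differ in their share of newly chronic patients, they are observed at different stages of therapy. The first-documentation outcomes, which carry the risk-mitigation part of Hypothesis 1 in SAP section 2, have no pre-period contrast to absorb either.

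**Working it through.** The plan gives no figure for this point, so there is none to reproduce. What can be computed is how far apart the windows lie and what that could do under stated assumptions.

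**Inputs.** The recruitment window is April 2019 to December 2021, 33 months (SAP 5). Rollout is described as "of intervention roll out in 5 steps that occurred in 3 to 4-month intervals between April 2019 and May 2020" (SAP 3). Five equally spaced starts over 13 months give s = 0, 3.25, 6.5, 9.75 and 13.

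**Assumptions.** Enrolment is even from each start to month 33, the five regions are weighted equally, and the control is already chronic when the control period opens. The SAP does not say whether that period opens by region, so three readings are shown:

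- A: both groups open by region.
- B: both groups open in April 2019.
- C: controls open in April 2019, CCM by region.

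| | A | B | C |
|---|---|---|---|
| Mean index gap (months) | mean of (33−s)/2 = 13.25 | 33/2 = 16.5 | mean of (s+33)/2 = 19.75 |
| Gap ≥12: post-index years do not overlap | mean of (21−s)/(33−s) = 53% | 21/33 = 64% | mean of (33−max(12,s))/(33−s) = 81% |
| Gap ≥24: CCM pre-index year starts after control post-index year ends | mean of max(0,9−s)/(33−s) = 11% | 9/33 = 27% | mean of 9/(33−s) = 35% |

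For example, the 53% is (0.636 + 0.597 + 0.547 + 0.484 + 0.400)/5, and the 81% is (0.636 + 0.706 + 0.792 + 0.903 + 1.000)/5.

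**First-documentation outcomes, no true effect (rates assumed).**

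- *Calendar difference.* Suppose new documentation among patients without a prior record is 20% in one window and 25% in the other. The odds ratio is (0.25/0.75)/(0.20/0.80) = 1.33, or 0.75 if reversed.
- *Steady drift.* If the odds rise by a factor of 1.1 a year, a gap of 16.5 to 19.75 months gives 1.1^(16.5/12) = 1.14 to 1.1^(19.75/12) = 1.17. A factor of 0.9 a year gives 0.87 to 0.84.
- *Stage of therapy.* Suppose 25% of controls and no CCM patients are newly chronic, with a rate 1.5 times an established 20%. The control rate is 0.75 × 0.20 + 0.25 × 0.30 = 22.5%, and the odds ratio is (0.20/0.80)/(0.225/0.775) = 0.86.

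**Repeated outcomes.** A common log-linear trend produces the same pre-to-post change wherever the window sits, so it cancels. A trend that levels off does not. Under assumed levelling falls in the odds of MEDD ≥50, the mildest case tested gives a change of 0.785 in controls and 0.848 in the later CCM windows, a null ratio of odds ratios of 0.848/0.785 = 1.08. The steepest gives 0.727/0.339 = 2.14.

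**Newly chronic patients and the dose average.** With about 90 covered days at index and an average over all 365 days, pre-index MEDD is 90/365 = 25% of the prescribed dose. Reaching 50 before index would need 50/0.247 = 203 MED a day, against about 50 after index if therapy continues. With 180 covered days the figures are 49% and 101 MED. If the average is over days on therapy, this dilution does not arise.

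**The case against.** No bias is demonstrated. A calendar gap matters only if outcomes also trend, and the documents report no primary-care trend. All index dates fall after the decision support became standard across the system in October 2017 (Protocol C.1). The primary outcome has both a difference-in-differences contrast and matching on pre-index dose. The overlap figures describe only controls already chronic at opening, whose share is unknown, and the odds ratios rest on assumed rates. The SAP describes MEDD as built from the total daily amount prescribed, which leans towards a dose on therapy and against dilution. Ninety covered days is also a floor, since earlier orders in the pre-index year are not excluded.

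Most of this stands as a limit on size. It does not remove the defect. The documents do not establish a flat documentation rate either; Protocol A.4 says in general terms that guideline uptake can be slow over years. The SAP's MEDD description does not settle the averaging denominator. For the first-documentation outcomes, the comparison depends on an unstated assumption that neither calendar date nor stage of therapy matters.

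**Conclusion.** The concern holds. The two index rules differ on the face of the SAP, and no matching variable or model term corrects for it. The exposure is plainest for the first-documentation outcomes. It is smaller for MEDD and utilisation, where bias needs trends that differ between the groups' windows or unequal newly chronic shares.

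Under even enrolment, equal regions and controls already chronic at opening, the index gap averages about 13 to 20 months and the post-index years do not overlap for 53% to 81% of CCM patients. Net bias cannot be sized or signed from the documents: calendar drift can push the odds ratio either way, and a larger newly chronic share among controls with higher first-documentation rates pushes it below 1. This should be corrected; confidence is medium, because the structural flaw is clear and its effect is not.

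**What to change.** - For each CCM patient, choose controls who, on that patient's enrolment date, meet the 90-of-120-day rule and are not enrolled in CCM. Use that date as the control's index.
- Add time since first meeting the rule to the propensity score, as far back as prescription history allows.
- State whether average MEDD is over all days or days on therapy, how controls who later enrol in CCM are handled, and whether matching is within region, since region sets when CCM becomes available.
- Report the distributions of index date and therapy duration by group. This alone would show how large the misalignment is.
- If dates cannot be closely aligned, add index date to the outcome models as a linear or spline term, with its interaction with time for repeated outcomes. Keep it low-dimensional rather than using quarter-by-time indicators.
- As a sensitivity analysis, restrict CCM patients to those meeting the 90-of-120-day rule at index, so that eligibility is the same in both groups.

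The cost is SAP wording and re-running the match and models on EMR data that are exported quarterly anyway (Protocol, Sources of Materials). The target of 578 does not change. The control pool looks sufficient. Protocol C.3.2 reports 2,759 chronic users, 71% with non-cancer pain and 62% with depression or anxiety. The number with both is at least 2,759 × (0.71 + 0.62 − 1) = 910, 1,215 if independent (2,759 × 0.71 × 0.62), and at most 2,759 × 0.62 = 1,711. Subtracting 289 CCM patients and dividing by 289 leaves 2.2, 3.2 or 4.9 potential controls each. That query is undated, covers 36 clinics, and precedes any score matching.

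The downsides are some lost close matches and a prescription look-back longer than 12 months. Much of SAP section 5 is written in the past tense; if the present match has already been analysed, report both analyses and label the aligned one post hoc.

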# STATISTICAL ANALYSIS PLAN

## 1. Introduction

**1.1 Study Design:** Type II effectiveness-implementation hybrid stepped wedged cluster randomized trial

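### The primary odds ratio is a non-randomised, matched comparison whose two groups are indexed by different date rules, so the stepped-wedge label does not describe the protection it has

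*SAP*

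**What the plan says.** SAP section 1.1 gives the design as "Type II effectiveness-implementation hybrid stepped wedged cluster randomized trial". SAP section 3 limits what was randomised: "each region (cluster) was randomized to the order". The five starts were spaced three to four months apart, the first in April 2019 and the last by May 2020. The same section adds that randomising clinics, providers or patients was not practical.

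Patients enter the intervention group by enrolling. Protocol C.4.3 shows the referral prompt only to physicians who agreed to take part. Protocol C.4.4 has patients referred by their primary care provider or opting in themselves.

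SAP section 5 draws controls from the chronic-opioid registry, "propensity score matched to patients enrolled in the behavioral health arm". The propensity score has seven patient-level variables: age, sex, race/ethnicity, average MEDD, anxiety, depression and Charlson score. The index dates follow two rules:

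- Intervention group: "the index date was defined as the date of enrollment during the study recruitment period (April 2019 to December 2021".
- Usual care: "the index date is the first date within the study enrollment period at which a patient had been prescribed opioid medications". The qualifying threshold is 90 days out of the preceding 120.

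For the repeated outcomes, which include the primary one: "The model included fixed effects for study group, time (pre-index, post-index), and the group-by-time interaction". The only random effect is at patient level. The secondary guideline-care outcomes have less: "The resulting logistic regression models include a single fixed effect for study group and no random effects". Protocol C.8.1 planned a comparison of enrolled with usual-care patients and said the models would account for design effects, without naming any.

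**The concern.** In a stepped-wedge analysis the randomised start dates decide who is exposed and when, and calendar-period terms remove secular change. Here exposure is set by referral, opt-in and matching. Region, roll-out step and calendar date appear in neither the propensity score nor a model. Time in the model means before or after each patient's own index date.

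The index rules add a specific weakness. A registry patient already on chronic therapy when the period opens is indexed at once, in April 2019, while enrollees can be indexed as late as December 2021. If high-dose prescribing changed abruptly or levelled off in between, the two groups would meet that change in different windows, and the group-by-time interaction could absorb it as if it were treatment. Patients readier to reduce their dose may also be likelier to accept referral; matching on baseline does not remove that. A reader who relies on the design label would credit the primary odds ratio with a protection it lacks.

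**Working it through.** **1. The planned effect.** SAP section 4 plans 10% against 20%. (0.20/0.80)/(0.10/0.90) = 2.25, as stated; in the direction of benefit this is 1/2.25 = 0.44. With equal baselines, 0.44 is also the planned ratio of odds ratios.

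**2. Calendar overlap.** April 2019 to December 2021 is 9 + 12 + 12 = 33 months. Roll-out ended in May 2020, and June 2020 to December 2021 is 19 months. So for 19/33 = 58% of recruitment no region is still waiting for the service. A control indexed in April 2019 has a post-index window of April 2019 to March 2020. An enrollee from April 2020 onward has a post-index window starting in April 2020 or later. They share no post-index month.

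**3. Could early-indexed controls be common?** Protocol C.3.2 reports 2,759 chronic-therapy patients in one 120-day query (36 clinics, before exclusions), against 289 controls needed. Early indexing therefore need not be rare. The query does not show who was matched or when they were indexed.

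**4. Illustration with no treatment effect. All of the following are assumptions.**

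- Enrollees: five equal regions starting at months 0, 3, 6, 10 and 13, each enrolling evenly to month 33.
- Controls: a share s indexed in April 2019, the rest spread evenly over the 33 months.
- Prevalence of MEDD ≥50 steps once, from 20% to 15%. The log-odds change is ln(0.15/0.85) − ln(0.20/0.80) = −0.348.

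Let f be the group's average share of the step that falls between its pre-index and post-index 12-month means. Then

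ratio of odds ratios = exp[−0.348 × (f for enrollees − f for controls)], with f for controls = s × f(early) + (1 − s) × f(even).

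| Step date | f enrollees | f even controls | f early controls | s = 0 | s = 0.5 | s = 1 |
|---|---|---|---|---|---|---|
| April 2019 | 0.080 | 0.197 | 1.0 | 1.04 | 1.20 | 1.38 |
| October 2019 | 0.212 | 0.326 | 0.5 | 1.04 | 1.07 | 1.11 |
| April 2020 | 0.357 | 0.364 | 0 | 1.00 | 0.94 | 0.88 |
| October 2020 | 0.444 | 0.364 | 0 | 0.97 | 0.91 | 0.86 |

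Example (April 2019, s = 1): exp[−0.348 × (0.080 − 1.0)] = exp(0.320) = 1.38. Enrollees' mean index date is 3.2, 11.2 and 19.2 months later than controls' for s = 0, 0.5 and 1.

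For a smaller step to 18%, the ranges are 0.97-1.07 (s = 0.5) and 0.94-1.13 (s = 1).

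**5. What cancels.** A trend linear in log-odds gives 1.00 at every s. So does a step in October 2017, when the decision-support tool went live (Protocol C.1 and C.4.1), because the earliest pre-index window opens in April 2018. If both groups have the same index dates, any trend common to all regions gives 1.00.

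**6. Room for a region model.** The present model has 4 fixed effects (intercept, group, time, interaction). Five regions add 4 main and 4 region-by-time terms, 12 in all. Expected events at 245 per group are 245 × (0.20 + 0.20 + 0.20 + 0.10) = 171.5 under the planned effect, or 490 × 2 × 0.20 = 196 with no effect. That is 171.5/12 = 14.3 to 196/12 = 16.3 events per parameter.

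**The case against.** The plan hides nothing. SAP section 3 says that only regional order was randomised and why, SAP section 5 describes the matching and both index rules, and Protocol C.8.1 planned enrolled against usual care. A reader might infer that a randomised analysis was quietly replaced; the documents do not support that. But planning and disclosing a non-randomised contrast does not make it randomised, and section 1.1 still carries the label without qualification.

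The size of the calendar effect is assumed. Neither s nor any dated step inside the window is in the documents, and the one dated system-wide primary-care change, in October 2017, cancels. The largest values (1.20, 1.38) need an abrupt fall right at April 2019 and would work against the intervention. Toward false benefit the illustration reaches only 0.91 or 0.86, far from 0.44. It also averages monthly log-odds, whereas the SAP dichotomises a 12-month average dose in a patient-level mixed model. All of this stands. A reader might infer that the primary result is biased toward the intervention, or largely an artefact; the documents support neither.

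The missing region term is a weaker complaint. Stable regional differences cancel in difference-in-differences, and region-specific trends cannot be sized from the documents. The model without random effects serves secondary outcomes only. Region therefore belongs in a sensitivity analysis.

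Finally, aligning dates leaves selection by referral or refusal in place, and SAP section 5 states the 90-of-120-day rule only for controls. Both are true. They limit what alignment achieves but do not argue for keeping unequal index rules.

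**Conclusion.** The point holds on the text and without any assumption: the primary odds ratio is a non-randomised, matched effect-of-enrolment estimate, and the randomised roll-out order contributes nothing to it. The two index rules also allow the groups' windows to cover different calendar periods, which difference-in-differences corrects only for stable differences and linear log-odds trends.

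The size and sign of any resulting bias are unknown. Under the assumed step from 20% to 15% it is small if no controls beyond an even spread are indexed early (0.97-1.04), and reaches 0.91-1.20 or 0.86-1.38 if half or all are. Selection on later change cannot be sized from the documents. The labelling must be corrected whatever the index-date distribution turns out to be; aligning the dates removes an avoidable source of bias.

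**What to change.** 1. State in the SAP and the report that the matched odds ratio is non-randomised and does not carry the protection of the stepped-wedge randomisation. Name selection through referral, opt-in and refusal as a remaining limitation. This costs only wording.

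2. Give each control the calendar index date of its matched enrollee, provided the control meets the 90-of-120-day rule on that date. Recompute the pre-index variables at that date and re-match.

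3. Report two sensitivity analyses: the SAP's present indexing, and a model with region and region-by-time (about 14-16 events per parameter at 245 per group).

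The re-dating and re-matching need more data work, but the records are already in the data warehouse. Some controls will not qualify on the assigned date, which shrinks the pool. After May 2020, date-aligned controls come from regions where the service was already available, so selection by non-referral or refusal stays. The SAP is written partly in the past tense; if results have already been seen, the change should be reported as made afterwards, with both analyses shown.
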